4.4.1 Inclusion Criteria

Potential patients are required to meet all of the following criteria for enrollment into the study and subsequent randomization:

- 1. Subjects must be at least 18 years of age or older.
- 2. Subjects must have a diagnosis of type 1 or 2 Diabetes mellitus.
- 3. At randomization subjects must have a target diabetic foot ulcer with a minimum surface area of 1.0 cm² and a maximum surface area of 20.0 cm² measured post debridement with a photographic planimetry app.
- 4. The target ulcer must have been present for a minimum of 4 weeks and a maximum of 52 weeks of standard of care prior to the initial screening visit.
- 5. The target ulcer must be located on the foot with at least 50% of the ulcer below the malleolus.
- 6. The target ulcer must be full thickness on the foot or ankle that does not probe to bone
- 7. Adequate circulation to the affected foot as documented by any of the following methods performed within 3 months of the first screening visit:
 - a. TCOM ≥30 mmHg
 - b. ABI between 0.7 and 1.3
 - c. PVR: Biphasic
 - d. TBI >0.6
 - e. As an alternative arterial Doppler ultrasound can be performed evaluating for biphasic dorsalis pedis and posterior tibial vessels at the level of the ankle.
- 8. If the subject has two or more ulcers, they must be separated by at least 2 cm. The largest ulcer satisfying the inclusion and exclusion criteria will be designated as the target ulcer.
- 9. Target ulcers located on the plantar aspect of the foot must be offloaded for at least 14 days prior to randomization.
- 10. The subject must consent to using the prescribed off-loading method for the duration of the study.
- 11. The subject must agree to attend the weekly study visits required by the protocol.
- 12. The subject must be willing and able to participate in the informed consent process.

Patients must have read and signed the IRB approved ICF before screening procedures are undertaken.

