4.5.3.1 TV1: Prior to Randomization

The following assessments and activities are performed at this visit:

- Medical history changes from previous visit
- Physical examination changes from previous visit
- Assess concomitant medications, changes from previous visit and prohibited therapies
- Vital Signs

Confidential Page 27 of 73

- Pain assessment (see section 8.9)
- Assess Blood glucose
- Index ulcer Assessments
- Assess signs and symptoms for clinical infection of the index ulcer (see section 8.10.3)
- Index ulcer foot neuropathy Semmes Weinstein 10-point test with vibratory; See section 8.14
- Clean the index ulcer
- Debridement of the index ulcer if applicable (see Appendix E)
- Digital imaging of the index ulcer
- Record Index ulcer measurements
- Assessment of offloading
- Index ulcer closure assessment will be determined by a site Investigator
 - If the index ulcer is 100% re-epithelialized, the subject will be considered a screen failure.
- Assessment of subject's eligibility to continue in the study
- SnapshotNIR (at selected sites)
- If the subject is eligible, randomization will be performed
- If the subject is not eligible, discharge the subject from the study as a screen failure

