9.2 Statistical Analysis

Descriptive statistical methods will be used to summarize the data from this study with hypothesis testing performed for the primary and other selected efficacy endpoints. All testing for endpoints will be two-sided with alpha set at .05 level of significance if no statistical testing is done at the interim analysis at 0.044 if statistical testing is done at N=240.

A formal Statistical Analysis Plan (SAP) will be created prior to database lock. The primary endpoint analysis will be at 12 weeks and a series of secondary and exploratory/tertiary

Confidential Page 49 of 73

endpoints will be analyzed at 6 and 12 weeks. The SAP will provide a more technical and detailed description of the proposed data analysis methods and procedures. Any deviation from the analyses outlined in the protocol will be described in the most current version of the SAP. All statistical analyses will be conducted using PASW 28.

The primary study hypothesis is that the proportion of wounds healed at 12 weeks, after up to 12 weeks of SOC with MIRRAGEN™ and SOC with FIBRACOL™, will be equal for Groups 1 and 2. Formally, H0: I1–I2 = 0; HA: I1–I2 = D1≠0, where I1 is the proportion of wounds healed in Group 1, I2 is same metric for Group 2, D1 is the difference (I1–I2); assuming the alternative hypothesis and statistical test used is chi square/Fisher exact test. Analysis may be adjusted using generalized linear modeling based on available variables at baseline known to affect wound healing.

Group sequential trials with sample sizes of 120 and 120 at the final look achieve 100% power to detect a difference of 0.35 between group 1 (the MIRRAGEN™ group) (proportion 0.70) the control group (SOC with FIBRACOL™) proportion of 0.35 at the 0.049 significance level (alpha) using a two-sided Z-Test (Pooled).

The populations defined for analysis will include the intent-to-treat (ITT) and per protocol (PP). Additional analysis populations may be defined to evaluate study results. Any additional analysis populations will be defined in the SAP.

Envelopes will be created with a random allocation sequence, which will be composed of a random sequence of block sizes of 10 designed to achieve a balanced design.

One interim analysis will be performed (N~100). The object of the interim analysis is to assess subject outcomes between the groups, in particular to assess any adverse effects or events, such as infection and to recalculate sample size for the primary endpoint.

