Primary analysis: Proportion of index wounds closed at 12 weeks (group 1 versus group 2) using chi square. Analysis will be adjusted using logistic regression.

Secondary analysis: (1) proportion of Index Wounds closed at 6 weeks (group 1 versus group 2) using chi square; (2) time to heal within 6 and 12 weeks using Kaplan-Meier analysis; (3) PAR at 6 and 12 weeks (group 1 versus group 2) using the Mann-Whitney test; (4) mean difference between groups 1 and 2 of change in weekly peripheral neuropathy score surrounding the DFU using the Semmes Weinstein monofilament with vibratory procedure based on GLM repeated measures; (5) mean difference between groups 1 and 2 of change in WOUND-Q score based on difference between baseline and 12 weeks using t test if data are normal or Kolmogorov–Smirnov test if data are non-normal; and (6) mean difference between groups 1 and 2 of change in weekly wound pain VAS score based on GLM repeated measures.

Control of the familywise error rate (all endpoints) will be achieved through the Hochberg stepup procedure.

Every effort will be made to obtain required data at each scheduled evaluation from all subjects who have been randomized and treated. Subjects who are withdrawn or lost to follow-up will be included in the ITT analysis of primary and secondary endpoints using data imputation methods detailed in the SAP. Sensitivity analysis will also be conducted for the primary endpoint using different imputation algorithms.

10 Adverse Effects and Events (Definitions and Reporting)

The Investigator is responsible for the detection and documentation of any events meeting the criteria and definition of an adverse effect or adverse event (AE), as described in this protocol.

Confidential Page 50 of 73

During the study when there is a safety evaluation, the Investigator or site staff will be responsible for detecting, documenting, and reporting any adverse effect or adverse event, as detailed in this Section of the protocol.

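### Time to heal and PAR are compared without baseline ulcer area, and no between-group test is named for time to heal; adjusting for log TV1 area is cheap and may help if the true effect is below design

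*Combined protocol and SAP*

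**What the plan says.** The secondary analyses in Section 9.2 list "time to heal within 6 and 12 weeks using Kaplan-Meier analysis" and "PAR at 6 and 12 weeks (group 1 versus group 2) using the Mann-Whitney test". Neither has a covariate or a stratum. Section 3 presents the secondary endpoints as comparisons between groups, yet neither Section 9.2 nor Table 4 gives a test or a treatment contrast for time to heal.

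Section 9.2 mentions adjustment twice. The primary-analysis paragraph states "Analysis will be adjusted using logistic regression". The primary-hypothesis paragraph states "Analysis may be adjusted using generalized linear modeling based on available variables at baseline known to affect wound healing". Neither sentence names a variable.

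Section 4.4.1 admits ulcers with a "minimum surface area of 1.0 cm² and a maximum surface area of 20.0 cm² measured post debridement with a photographic planimetry app". Section 4.5.3.1 lists "Record Index ulcer measurements" among the TV1 procedures before randomization, so baseline area will exist for every randomized subject. It is also the denominator of PAR (Section 3). Allocation in Section 9.2 is by blocks of 10, with no stratification by area stated. Multiplicity over all endpoints is handled by the Hochberg procedure, and a formal SAP is still to be written before database lock.

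**The concern.** The plan accepts that baseline variables affect healing and adjusts the primary analysis, but it does not carry this over to the two secondary endpoints most directly tied to ulcer size. If wound edges advance at a constant rate, closure time is proportional to the radius, so a 20 cm² ulcer takes √(20/1) = 4.47 times as long to close as a 1 cm² ulcer. PAR would also depend on size: with edge speed v and radius R, the area fraction left at time t is (1 − vt/R)², so percentage reduction falls as R rises.

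Three things are at stake: precision if the treatment effect is smaller than designed, the sensitivity of the estimates to a chance imbalance in ulcer size, and the absence of any stated effect measure for time to heal. Under Hochberg, a missed endpoint also makes the thresholds for the remaining endpoints stricter.

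**Working it through.** **Inputs from the plan.** Section 9.2: 120 per arm, 0.70 v 0.35 healed, two-sided alpha 0.049, pooled Z-test. Section 4.4.1: area 1 to 20 cm². Sections 3 and 4.3.1: 12 weeks, weekly visits.

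**Assumptions, not in the documents.** Log area uniform from ln 1 to ln 20; a smaller true effect of 0.50 or 0.525 v 0.35; the prognostic strength of area; for PAR, a standardized difference d = 0.37 and a correlation r between area and PAR.

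**1. The plan's own figure.** The pooled proportion is 0.525.
- Null SE = √(2 × 0.525 × 0.475/120) = 0.0645.
- Alternative SE = √((0.70 × 0.30 + 0.35 × 0.65)/120) = 0.0604.
- Power = Φ((0.35 − 1.969 × 0.0645)/0.0604) = Φ(3.69) = 0.9999.

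The stated 100% reproduces. It is also 0.9999 at alpha 0.05 and at 0.044.

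**2. Time to heal at the design effect, no covariate.** With exponential healing, HR = ln 0.30/ln 0.65 = 2.79, with 120 × (0.70 + 0.35) = 126 events. Power = Φ(ln 2.79 × √(126/4) − 1.969) = Φ(3.80) = 0.9999. At 0.05/7 (one primary and six secondary analyses, the strictest Hochberg step) it is 0.999. There is nothing left for a covariate to add.

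**3. Time to heal at 0.525 v 0.35, constant hazards.** Cox model with treatment only, then with log area added; 2,000 simulated trials per row, alpha 0.049:

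| Fall in healing hazard per SD of log area | Unadjusted | Adjusted |
|---|---|---|
| none | 0.78 | 0.78 |
| factor 1.25 | 0.78 | 0.79 |
| factor 1.5 | 0.76 | 0.80 |
| factor 2.0 | 0.79 | 0.88 |

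At 0.50 v 0.35, factor 2.0 gives 0.64 to 0.75 and no effect of area gives 0.66 to 0.65. At 0.70 v 0.35 every row is 1.00, with or without area.

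**4. Edge-advance model at 0.50 v 0.35.** Closure time is proportional to a power of area; the power 0.5 is constant edge advance. The SD is that of log healing rate between ulcers. There were 500 trials per setting for the power 0.5 and 300 otherwise, with no Hochberg correction. PAR is at 6 weeks, Mann-Whitney then rank-adjusted.

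| Power of area | SD | Time to heal | PAR |
|---|---|---|---|
| 0.5 | 0.4 | 0.74 to 0.94 | 0.87 to 0.99 |
| 0.5 | 0.6 | 0.73 to 0.86 | 0.86 to 0.96 |
| 0.5 | 0.8 | 0.69 to 0.75 | 0.82 to 0.91 |
| 0.5 | 1.2 | 0.70 to 0.73 | 0.82 to 0.86 |
| 0.25 | 0.4 | 0.68 to 0.74 | 0.84 to 0.92 |
| 0.25 | 0.8 | 0.69 to 0.72 | 0.84 to 0.85 |
| 0.1 | 0.4 | 0.65 to 0.67 | 0.82 to 0.82 |
| 0.1 | 0.8 | 0.67 to 0.67 | 0.84 to 0.84 |

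For constant edge advance, separate runs put the gain at 7 to 22 points for time to heal and 9 to 14 for PAR. At 0.70 v 0.35 (SD 0.4 and 0.8) all four analyses had simulated power of 1.000. Under the null (SD 0.6, 800 trials) all four rejected in 0.035 to 0.051 of trials.

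**5. PAR by formula.** Mann-Whitney efficiency is taken as 3/π, so the effective n per arm is 120 × 0.955 = 114.6. Unadjusted power = Φ(0.37 × √(114.6/2) − 1.969) = Φ(0.83) = 0.797. Adjustment multiplies the residual SD by √(1 − r²). For r = 0.1, 0.2, 0.3, 0.4 and 0.5 power becomes 0.801, 0.813, 0.833, 0.862 and 0.897. At r = 0.5, 240 adjusted subjects carry the information of 240/0.75 = 320 unadjusted ones.

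**6. Chance imbalance.** Under the assumed area distribution the SD of log area is ln 20/√12 = 0.865, so the SE of the difference in means is 0.865 × √(2/120) = 0.112. A difference above 0.11 (about 12% in geometric-mean area) is about one SE and arises in about 16% of trials in each direction. At 0.70 v 0.35 (constant edge advance, SD 0.6, 200 trials) the average unadjusted hazard ratio in such trials was 2.65 when the MIRRAGEN ulcers were larger and 3.44 when they were smaller.

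**Limits.** The simulation in step 3 leaves out dropout and the week-7 exit. PAR at 12 weeks was not simulated.

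**The case against.** The strongest reply is that nothing is lost at the effect the trial was designed for, and that 0.50 v 0.35 appears nowhere in the plan. That stands. A reader might infer that the plan gives power away under its own assumptions; steps 1, 2 and 4 show that it does not. The smaller effect is a what-if. It is worth asking because the rationale rests on a 40-patient pilot and Section 9.2 itself foresees an interim recalculation of sample size.

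Second, the large gains come from models that make area strongly prognostic by construction: under constant edge advance the rank correlation of area with 6-week PAR was −0.46 to −0.72. The documents give neither the strength of this relation nor the distribution of area, and PAR is already scaled to TV1 area, so only the remaining correlation helps. This stands too, and the range must therefore start at zero.

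Third, unadjusted Kaplan-Meier and Mann-Whitney comparisons are valid in a randomized trial, and their type I error already allows for chance imbalance. Correct: a reader might infer bias or invalid tests, and the documents support neither.

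Fourth, the optional-adjustment sentence in Section 9.2 is not expressly confined to the primary endpoint, and detail is deferred to the SAP. So the plan does not rule adjustment out. But the sentence sits in the primary-hypothesis paragraph, is permissive and names no variable, so as written it commits to nothing for these two endpoints.

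**Conclusion.** The point holds as an efficiency and estimation improvement, not as an error in the plan. Time to heal has no named between-group test or effect estimate, and neither it nor PAR uses the TV1 area that will be on file.

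At 0.70 v 0.35 the gain in power is nil. At an assumed 0.50 to 0.525 v 0.35 it runs from about 0 points (area not or only weakly prognostic) to about 20 points (constant edge advance) for time to heal, and from about 0 to about 14 points for 6-week PAR. These ranges rest on the assumed effect, area distribution and prognostic strength, and they do not include the Hochberg correction at the smaller effect. The lower sensitivity to chance imbalance applies even at the design effect, provided area is prognostic.

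A reader might also infer from the inclusion rule "The target ulcer must have been present for a minimum of 4 weeks and a maximum of 52 weeks" that ulcer duration must be a covariate. The range shows spread, not prognostic value, and no calculation here tested duration.

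**What to change.** In Section 9.2, secondary analysis (2), make the comparison of time to heal a Cox model with treatment and log TV1 area, reporting the hazard ratio with its confidence interval, and keep the Kaplan-Meier curves for display. In secondary analysis (3), replace the Mann-Whitney test by rank ANCOVA on TV1 area, or by a van Elteren test stratified by area with the cut-points fixed in advance. Ulcer duration may be added but is optional. Carry the same wording into the SAP, and name the covariate now, since the trial is open label and a later choice would be open to question.

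The cost is wording only, with no new data. Proportional hazards must be checked, and the SAP should say what is reported if the assumption fails. The adjusted hazard ratio is conditional on area and will generally lie further from 1 than the unadjusted one: for the same 0.70 v 0.35, the constant-hazards model gives 2.79 with no area effect and 3.40 at factor 2.0 per SD. The report should state which of the two it presents.

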- Assess concomitant medications, changes from previous visit and prohibited therapies
- Vital signs
- Pain assessment (see section 8.9)
- Assess blood glucose
- Index ulcer assessment
- Assess signs and symptoms for clinical infection of the index ulcer (see section 8.10.3)
- Index ulcer foot neuropathy Semmes Weinstein10 point test with vibratory; See section 8.14
- Clean the index ulcer
- Debridement of the index ulcer if applicable (see Appendix E)
- Digital imaging of the index ulcer
- Record Index ulcer measurements
- Assessment of offloading
- Assessment of subject's eligibility to continue in the study
- Apply appropriate SOC to index ulcer and outer dressing

A panel of three board-certified plastic surgeons will review each wound, as well as inclusion/exclusion criteria, in a blinded fashion to ensure that randomizations are appropriate. The review will occur between SV2 and the day of randomization. The plastic surgeon will provide correspondence to the trial manager that the subject is appropriate for randomization, prior to the site being able to randomize the patient.

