8.9 Pain Assessment: NPRS

Pain intensity of the reference DFU is to be assessed before any dressing changes or other ulcer manipulations at all screening and treatment visits.

The subject will be asked to indicate a numerical value that best represents the current pain intensity at the index ulcer site on a scale of 0 to 10, anchored by word descriptors at each end, as "no pain" on the left side and "worst possible pain" on the right side of the number line. The number 0 represents "no pain," the number 5 represents "moderate pain", and the number 10 represents the "worst possible pain." The subject indicates the level of pain intensity by selecting a number on the line shown in Figure 3 below that represents their perception of their current state.

[figure not shown]

FIGURE 3: SUBJECT PAIN SCALE (NPRS)

Confidential Page 45 of 73

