9.1 Data Analysis

This study consists of primary, secondary and exploratory/tertiary (research) endpoints. Data analysis of study endpoints includes use of validated DFU wound healing measures, quantitative and qualitative analyses, as well as exploratory methodologies. Table 4 below details each study endpoint, corresponding data, and planned analyses.

TABLE 4: ETS WOUND CARE, LLC DFU ENDPOINT DATA ANALYSIS

Endpoint	Endpoint Description	Supporting Study Data	Endpoint Analysis
Primary	Comparison of the proportion of index ulcers "healed" at 12 weeks	Investigator assessment of healing (100% epithelization w/no drainage), measurements of ulcer size using digital imaging and photos	Adjudication panel will determine using photographs of the DFU
	Proportion of Index Ulcers healed at 6 weeks		
	PAR at 6 and 12 weeks	Digital imaging	Mathematical wound area change
	Time to healing within 6 and 12 weeks	Primary endpoint	Mathematical time based on healing
Secondary	Changes in peripheral neuropathy	Semmes Weinstein with vibratory	Mathematical change in scores
	Changes in wound quality of life	WOUND-Q (Quality of life tool)	Mathematical change in scores
	Change in pain levels during trial	NPRS	Mathematical change in scores
	Difference in cellulitis and/or infection at 12 weeks	Observation	Count of positive and negative responses
Exploratory/Tertiary	Changes in tissue perfusion of wound bed and periphery with treatment	SnapshotNIR	Exploratory

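### Secondary analyses (4) and (6) compare change in neuropathy and pain and state no adjustment for the baseline score, which gives up precision at no saving

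*Combined protocol and SAP*

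**What the plan says.** Section 9.2 lists six secondary analyses. Item (4) takes the "mean difference between groups 1 and 2 of change in weekly peripheral neuropathy score surrounding the DFU", analysed by repeated-measures GLM. Item (6) is the "mean difference between groups 1 and 2 of change in weekly wound pain VAS score based on GLM repeated measures". (Item (6) says VAS where section 8.9 and the endpoint list use the NPRS; I take them to be the same score.) Table 4 in section 9.1 describes the analysis of both endpoints only as "Mathematical change in scores".

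Neither item names a covariate. Adjustment appears twice elsewhere in section 9.2. For the primary analysis, "Analysis will be adjusted using logistic regression". After the primary hypothesis, "Analysis may be adjusted using generalized linear modeling based on available variables at baseline known to affect wound healing". The second sentence is optional and concerns predictors of healing, not the baseline value of a pain or sensation score. Further detail is deferred: "The SAP will provide a more technical and detailed description of the proposed data analysis methods and procedures".

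Both scores are available before randomization. Pain "is to be assessed before any dressing changes or other ulcer manipulations at all screening and treatment visits" (section 8.9). The procedure list for SV2 includes "Index ulcer foot neuropathy Semmes Weinstein10 point test with vibratory", and the lists for SV1 (section 4.5.2) and for TV1 before randomization (section 4.5.3.1) include the same test. The time frame for both endpoints in section 3 starts at TV1 and continues with TV3, TV7, TV9 and EOS1. Section 9 does not say which visit is the baseline for the change.

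**The concern.** A change score subtracts the whole TV1 value, including its measurement noise and its ordinary fluctuation from visit to visit. Unless scores at different visits are almost perfectly correlated, that subtracts too much. Regression on the baseline score subtracts only the part that predicts the later score, and in large samples its variance is never higher. A baseline difference that arises by chance is over-corrected by the change score and correctly discounted by regression.

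At stake are wider confidence intervals and lower power on two tested secondary endpoints than the collected data allow.

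**Working it through.** **Inputs.** The documents give no standard deviation, correlation, effect size or power for pain or neuropathy, so there is no planned figure to reproduce. The standard deviation cancels in a variance ratio. The follow-up visits (TV3, TV7, TV9, EOS1) come from section 3, and the 120 per group from section 9.2. The correlation rho between any two visits is an assumption, shown from 0.3 to 0.9. Variances are assumed equal at all visits and rho the same for every pair.

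**Formulas.** Variance per subject, in units of the score variance, for the mean of r follow-up visits:

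- change from TV1: V_change = (1 + (r − 1)rho)/r + 1 − 2rho
- adjusted for TV1: V_adj = (1 + (r − 1)rho)/r − rho²

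The difference is (1 − rho)². V_change simplifies to (r + 1)(1 − rho)/r, so the proportional cut is r(1 − rho)/(r + 1). That is (1 − rho)/2 for one visit and 0.8(1 − rho) for four.

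**Results.**

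| rho | One visit: change | One visit: adjusted | Cut | Four visits: change | Four visits: adjusted | Cut |
|---|---|---|---|---|---|---|
| 0.3 | 1.40 | 0.91 | 35% | 0.875 | 0.385 | 56% |
| 0.5 | 1.00 | 0.75 | 25% | 0.625 | 0.375 | 40% |
| 0.7 | 0.60 | 0.51 | 15% | 0.375 | 0.285 | 24% |
| 0.9 | 0.20 | 0.19 | 5% | 0.125 | 0.115 | 8% |

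For other numbers of visits at rho 0.5, two visits give 2(0.5)/3 = 33% and twelve weekly visits give 12(0.5)/13 = 46%.

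**Check.** A simulation with 240 subjects, one follow-up visit and rho 0.5 (20,000 runs) gave a variance ratio of 0.74 for adjustment on TV1, against 0.75 from the formula.

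**What this means for power.** Assume a true difference of 0.35 SD, 120 per group, two-sided 0.05, one visit and rho 0.5.

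- Change: 0.35/√(2 × 1.00/120) = 2.71, and 2.71 − 1.96 = 0.75, power 77%.
- Adjusted: 0.35/√(2 × 0.75/120) = 3.13, and 3.13 − 1.96 = 1.17, power 88%.

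The 0.35 SD is purely illustrative.

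**The case against.** **The SAP may supply the covariate.** A repeated-measures GLM accepts covariates, and the detailed SAP is still to be written. A reader might infer that the plan rules out baseline adjustment. It does not; it is silent. That silence still matters, because the trial is open label, has an interim analysis at about 100 subjects, and requires the SAP only before database lock. A covariate chosen that late could look as if it had been chosen from the data.

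**The contrast is not stated.** The four-visit average is one reading. Section 9.2 also says that secondary endpoints are analysed at 6 and 12 weeks, which points to single visits, and a group-by-time test with TV1 as a repeated level is possible too. Subjects with less than 50% area reduction leave at TV7, and healed subjects reach EOS1 early, so many will not have four follow-up visits. This objection stands. It is why the single-visit figure comes first and the 40% is conditional.

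**The correlation is assumed, and one value serves two different outcomes.** This also stands. If scores are very stable, the gain is only 5% to 8%.

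**Three stronger readings are not supported.**

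- *That the change score biases the treatment effect.* Under randomization it does not; the loss is one of precision.
- *That the three pre-randomization measurements make the cost of not adjusting much larger.* At rho 0.5 with four follow-up visits, adjusting for the mean of SV1, SV2 and TV1 gives a variance of 0.25, which is 60% below change from TV1. Most of that comes from averaging the baselines. Change from the same three-visit mean already has variance 0.292, so adjustment itself saves about 14%. The three visits are also not clearly interchangeable, since protocol standard of care and offloading start at SV1 (sections 4.5.2 and 7).
- *That the primary analysis or the sample size is affected.* Closure has no baseline value, and the sample size rests on closure alone.

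**Conclusion.** The point holds as a loss of precision on two secondary endpoints. As written, items (4) and (6) of section 9.2 compare change scores and state no adjustment for the baseline score, while a baseline score taken before randomization is available for both. At an assumed correlation of 0.5, adjusting for TV1 lowers the variance by 25% for a single visit and by 40% for the average of the four listed follow-up visits. Over correlations from 0.3 to 0.9 the ranges are 35% to 5% and 56% to 8%. These figures rest on equal variances, one common correlation, complete follow-up at the visits averaged, and change being taken from TV1, which the endpoint time frame suggests but section 9 does not state. The direction does not depend on the value of rho: under this model the saving is positive for any correlation below 1. The change is worth making because it costs almost nothing; the trial's main conclusion does not depend on it.

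**What to change.** In section 9.2, items (4) and (6), and in the SAP:

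- Define baseline as the TV1 score recorded before randomization.
- Compare the follow-up scores between groups in a repeated-measures model with treatment, visit, treatment-by-visit and the TV1 score as covariate. TV1 must not also be an outcome level, or the same value would be used twice.
- State which contrast is the test: the average over named visits, or specific visits.
- Report the adjusted between-group difference with its 95% CI.

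The cost is a few lines of text and one extra model term per endpoint. No new data, visits or subjects are needed. The change should be fixed before any comparative data are seen.
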